## STATEMENT OF COMPLIANCE

The trial will be carried out in accordance with International Conference on Harmonisation Good Clinical Practice (ICH GCP) and the following:

- United States (US) Code of Federal Regulations (CFR) applicable to clinical studies (45 CFR Part 46, 21 CFR Part 50, 21 CFR Part 56, 21 CFR Part 312, and/or 21 CFR Part 812)

National Institutes of Health (NIH)-funded investigators and clinical trial site staff who are responsible for the conduct, management, or oversight of NIH-funded clinical trials have completed Human Subjects Protection and ICH GCP Training.

The protocol, informed consent form(s), recruitment materials, and all participant materials will be submitted to the Institutional Review Board (IRB) for review and approval. Approval of both the protocol and the consent form must be obtained before any participant is enrolled. Any amendment to the protocol will require review and approval by the IRB before the changes are implemented to the study. In addition, all changes to the consent form will be IRB-approved; a determination will be made regarding whether a new consent needs to be obtained from participants who provided consent, using a previously approved consent form.]

## 1 PROTOCOL SUMMARY

### 1.1 SYNOPSIS

Title:	Evaluation of an Interdisciplinary Decision Guide for Infant Feeding Assessment
Study Description:	This study will determine if a decision support tool changes clinical practice recommendations when used by speech language pathologists and occupational therapists. We hypothesize the support tool will change whether providers will recommend specialist referral.
Objectives:	Primary objectives are the degree of concordance in feeding therapy, referral, and specific specialist referral recommendations between therapists using and not using the tool. Secondary objectives include degree of concordance between feeding therapy frequency and therapy target recommendations as well as acceptability, appropriateness, and feasibility of the tool.
Endpoints:	The endpoint is when the provider has finished reading the case study.
Study Population:	56 speech language pathologists and occupational therapists with at least two years of feeding experience and currently practicing in North Carolina
Phase:	N/A
Description of Sites/Facilities Enrolling Participants:	This study will occur through an online survey. Survey recruitment will be based out of UNC-Chapel Hill.
Description of Study Intervention:	The study intervention is a decision support tool, which is a checklist of signs and symptoms of feeding problems.
Study Duration:	The estimated duration is 6 months.

**Participant Duration:** Participants will take about 20 minutes to complete an initial interest survey and then the full survey.

## 1.2 SCHEMA

## Ongoing

### Screening

- Total n=70
- Screen potential participants by inclusion and exclusion criteria through an online survey

## Ongoing

### Randomization

- Case A, then Case B group (n=28)
- Case B, then Case A group (n=28)

## Ongoing

### Study Intervention

- Participants complete informed consent
- Participants complete survey and demographic information

### 1.3 SCHEDULE OF ACTIVITIES (SOA)

Procedures	Screening Day -7 to -1	Enrollment/Baseline Day 1	Survey Day 1 – Day 14
Screening	X		
Randomization		X	
Informed Consent			X
Administer study intervention			X
Demographic Information			X

## 2 INTRODUCTION

### 2.1 STUDY RATIONALE

While it is now recognized that pediatric feeding disorder (PFD) involves medical, nutritional, feeding skill, and/or psychosocial domains [1], in early intervention (EI) in North Carolina, individual providers (speech language pathologists (SLPs) or occupational therapists (OTs), are tasked with individually assessing and treating infants with PFD. While trained in feeding skills and sensory processing, these professionals are also expected to screen the medical, nutritional, and psychosocial domains, and make appropriate external referrals, despite these areas being outside of their scope of practice. The importance of a thorough, systematic evaluation and referral process is particularly important at the transition to solid foods, a critical developmental juncture as feeding demands increase and nutritional needs shift [15,16]. SLPs and OTs in EI need a tool that facilitates timely referrals and communication with multidisciplinary feeding teams, or individual specialists, when assessing infants with PFD.

### 2.2 BACKGROUND

Pediatric feeding problems fall within the scope of many professionals; speech-language pathologists (SLPs), occupational therapists (OTs), nurses, dietitians, gastroenterologists, pediatricians, and psychologists/behavior analysts may be involved in evaluation and treatment. In 2019, a consensus definition of pediatric feeding disorder (PFD) was published, providing these professionals with common diagnostic criteria [1]. Preterm infants (1 in 10 live births in North Carolina), are particularly at risk for long-term PFD, representing up to 40% of children seen at feeding disorder clinics [2,3]. The resulting economic impact is significant; even insured families report an average loss of \$125,645 in income caring for their child with PFD [4].

While it is now recognized that PFD involves medical, nutritional, feeding skill, and/or psychosocial domains, in early intervention (EI) in NC, individual SLP or OT providers assess and treat infants with PFD. While trained in feeding skills and sensory processing, these providers are also expected to screen the medical, nutritional, and psychosocial domains and make appropriate referrals, despite these areas being outside of their scope of practice. The importance of a multi-domain, systematic evaluation and referral process is particularly important for preterm infants. Preterm infants are likely to present symptoms relevant to multiple professionals including gastroesophageal disorders, physiologic

instability, nutritional deficits, and behavior problems into early childhood [5–12]. This is particularly true at the transition to solid foods, a critical developmental juncture as feeding demands and nutritional needs shift [13,14]. EI SLPs and OTs need a tool to facilitate timely referrals and communication with other specialists when assessing preterm infants with PFD.

We propose the development of a decision-making tool for the evaluation of preterm infants with PFD by SLPs and OTs in EI to facilitate appropriate external referrals. This tool is specific to children at the solid food level (6mo-3years) and is called the Clinical Feeding Guide (CFG). We have developed a list of observational items through examination of existing tools and a literature review. To achieve our goal of developing a feasible clinical tool, we will pursue the following specific aims. Aim 1: Establish content validation using the Delphi Technique to generate a screening and decision-making tool. Aim 2: Complete pilot testing of the tool to determine feasibility, acceptability, and change from current standard practice.

## 2.3 RISK/BENEFIT ASSESSMENT

### 2.3.1 KNOWN POTENTIAL RISKS

There are no known risks of using the intervention, as it is being used on mock case studies. There is the potential for participants to experience emotional distress or consequences of a breach of confidentiality. Although the likelihood of a breach of confidentiality is low, the data collected could yield information about participants' behaviors and demographics that could cause emotional distress if confidentiality were breached. Professionals may also experience fatigue, frustration, or stress will reading case studies. However mock case studies have been determined to yield the least stress over considering real cases or viewing videos of real children.

### 2.3.2 KNOWN POTENTIAL BENEFITS

This study does not have any potential for direct benefit to the individual subjects in this study. However, we do hope that the tool developed will benefit infants and professionals in the future by improving clinical practice and the accurate and timely diagnosis and treatment of feeding disorders in infants and children.

### 2.3.3 ASSESSMENT OF POTENTIAL RISKS AND BENEFITS

This study will contribute to our understanding about how SLPs and OTs make appropriate external referrals during clinical feeding evaluations. It is necessary for SLPs and OTs to test this tool in order to understand its potential impact. Risks to participants have been minimized by de-identifying participant responses, reporting participant responses as an aggregate, and having participants read short, mock case studies while using the tool. These limited risks outweigh the value of the information to be gained, which would assist professionals in making better clinical decisions thereby improving the treatment of feeding problems in infants.

## 3 OBJECTIVES AND ENDPOINTS

OBJECTIVES	ENDPOINTS	JUSTIFICATION FOR ENDPOINTS
Primary		

OBJECTIVES	ENDPOINTS	JUSTIFICATION FOR ENDPOINTS
Degree of Concordance Between Therapists' Feeding Therapy Recommendations	After reading a feeding case study, early intervention professionals will answer the question "Would you recommend feeding therapy?" with two choices: yes or no. Difference in agreement between early intervention professionals using the decision support tool and those not will be calculated and compared for cases A and B.	To determine whether using the tool, which helps identify feeding problem symptoms, changes decisions therapists make around recommending therapy for a child.
Degree of Concordance Between Therapists' Referral Recommendations	After reading a feeding case study, early intervention professionals will answer the question "Would you refer this family to any other providers/specialists for evaluation/treatment?" with two answer choices: yes or no. Difference in agreement between early intervention professionals using the decision support tool and those not will be calculated and compared for cases A and B.	To determine whether using the tool, which helps identify feeding problem symptoms by discipline with the explicit purpose of facilitating referrals, changes decisions therapists make around recommending referral to a specialist.
Degree of Concordance Between Therapists' Specific Specialist Referral Recommendations	After reading the feeding case study, early intervention professionals will answer the question "What other professionals would you refer this child to? Check all that apply." with the following choices: nutritionist/dietician, gastroenterologist, otolaryngologist (ENT), aerodigestive clinic, pulmonologist, occupational therapist, speech language pathologist, psychologist/social worker, applied behavior analyst (ABA), or allergist. Difference in agreement between early intervention professionals using the decision support tool and those not will be calculated and compared for cases A and B.	To determine whether the tool, which lists feeding problem symptoms by specialist discipline, changes the specialists a therapist refers to.
Secondary		

OBJECTIVES	ENDPOINTS	JUSTIFICATION FOR ENDPOINTS
Degree of Concordance Between Therapists' Feeding Therapy Frequency Recommendations	After reading the feeding case study, early intervention professionals who recommended feeding therapy will answer the question "With what frequency would you recommend therapy?" with three choices: 2 times per week or more, 1 time per week, less than one time per week. Difference in agreement between early intervention professionals using the decision support tool and those not will be calculated and compared for cases A and B.	To determine whether using the tool, which helps identify feeding problem symptoms, changes decisions therapists make around recommending a specific frequency of therapy for a child.
Degree of Concordance Between Therapists' Intervention Target Choices	After reading the feeding case study, early intervention professionals who recommended feeding therapy will answer the question "What therapy targets might you include for this child?" and may check all that apply from the following choices: oral motor skills, sensory, behavioral, medication, modification of food/liquid, modification of equipment (seating, utensils, etc.), modification of environment (location, distractions, routine, etc.), parent coaching, or other. Difference in agreement between early intervention professionals using the decision support tool and those not will be calculated and compared for cases A and B.	To determine whether using the tool, which helps identify feeding problem symptoms by area of concern, changes decisions therapists make around recommending a specific intervention target for a child.
Decision Support Tool Acceptability Score	The Acceptability of Intervention Measure (AIM) will be used to measure acceptability of the decision support tool. This tool includes four items, rated on a five-point Likert scale from completely disagree to completely agree, and will be quantified with a score of 0 for completely disagree, 1 for disagree, 2 for neither agree nor disagree, 3 for agree, and 4 for completely agree. The average score across the four items will be calculated, with higher	To determine if this intervention is acceptable to practicing therapists.

OBJECTIVES	ENDPOINTS	JUSTIFICATION FOR ENDPOINTS
	scores indicating higher acceptability of the decision making tool. The minimum score is 0 and the maximum score is 20. Items on this measure include: (Intervention) meets my approval; (Intervention) is appealing to me; I like (Intervention) and I welcome (Intervention).	
Decision Support Tool Appropriateness Score	The Intervention Appropriateness Measure (IAM) will be used to measure appropriateness of the decision support tool. This tool includes four items, rated on a five-point Likert scale from completely disagree to completely agree, and will be quantified with a score of 0 for completely disagree, 1 for disagree, 2 for neither agree nor disagree, 3 for agree, and 4 for completely agree. The average score across the four items will be calculated, with higher scores indicating higher acceptability of the decision making tool. The minimum score is 0 and the maximum score is 20. Items on this measure include: (Intervention) seems fitting; (Intervention) seems suitable; (Intervention) seems applicable; (Intervention) seems like a good match.	To determine if practicing therapists feel this intervention is appropriate for the preterm, early intervention population and to the therapists.
Decision Support Tool Feasibility Score	The Feasibility of Intervention Measure (FIM) will be used to measure feasibility of use of the decision support tool. This tool includes four items, rated on a five-point Likert scale from completely disagree to completely agree, and will be quantified with a score of 0 for completely disagree, 1 for disagree, 2 for neither agree nor disagree, 3 for agree, and 4 for completely agree. The average score across the four items will be calculated, with higher scores indicating higher acceptability of the	To determine if therapists feel this intervention is feasible to use in clinical practice.

OBJECTIVES	ENDPOINTS	JUSTIFICATION FOR ENDPOINTS
	decision making tool. The minimum score is 0 and the maximum score is 20. Items on this measure include: (Intervention) seems implementable; (Intervention) seems possible; (Intervention) seems doable; (Intervention) seems easy to use.	
Tertiary/Exploratory		
N/A	N/A	N/A

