## 6 STUDY INTERVENTION

### 6.1 STUDY INTERVENTION(S) ADMINISTRATION

### 6.1.1 STUDY INTERVENTION DESCRIPTION

The study intervention is a checklist that was developed with feeding specialists at UNC Health through Delphi surveys. The checklist contains four headings: gastrointestinal, nutritional, behavioral, and aerodigestive. Under each heading there is a list of observable symptoms that may warrant referral to a specialist provider in that area.

The main heading says, “Feeding Assessment Referral Guide”. The main subheading says, “Use the following checklist during the feeding evaluation to observe symptoms that may warrant referral to specialists.”

Under gastrointestinal, the observable symptoms are:

- Frequent spitting up/vomiting during meal
- Fussiness, crying, or arching during meal
- Wheezing, stridor, cough, or hoarseness while eating
- Gagging during meal
- Burps frequently while eating
- Drools while eating
- Avoidance or prioritizing of certain food textures

Under aerodigestive, the observable symptoms are:

- Gets red in the face while eating
- Coughs during meal
- Food/liquid comes out nose while eating
- Gets tired and cannot finish eating
- Breathes harder/faster while eating
- Evidence of stridor v. stertor
- Needs to pause during meal to catch breath
- Watery eyes while eating

Under behavioral, the observable symptoms are:

- Refuses to eat
- Whines, cries, or tantrums during meal
- Insists on food being offered a specific way
- Throws or pushes food away
- Will not stay seated during meal
- Throws or spits food
- Parent has to do something special to get child to eat
- Parent and child have conflict during feeding
- The parent appears stressed and overwhelmed during feeding

Under nutrition, the observable symptoms are:

- Appears underweight
- Exclusion of entire food group
- Eating only one texture of food during evaluation

At the bottom, the checklist says, “If the child has demonstrated any of these signs/symptoms while eating, referral to a medical specialist, in addition to your treatment, may be warranted.”

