# 8 STUDY ASSESSMENTS AND PROCEDURES

## 8.1 EFFICACY ASSESSMENTS

To test intervention efficacy, the participant will be asked to answer a set of clinical questions after reading the case study. They will first do this without the intervention and then read another case study using the intervention. This will be administered through Qualtrics in survey form.

The questions include:

- Would you recommend feeding therapy to this child? Yes/No
  - If yes, "With what frequency would you recommend therapy?"
    - 2 times per week, 1 time per week, Less than one time per week
  - If yes, "What therapy target areas might you include for this child?" (select all that apply)

- Oral motor skills, sensory, behavioral, medication, modification of food/liquid, modification of equipment (seating, utensils, etc.), modification of environment (location, distractions, routine, etc), parent coaching, other (fill in)
- If yes, "What would be the recommended length of treatment for this child?"
  - Less than 6 months, 6-12 months, More than 12 months
- What diagnosis would you give this child?
- Would you refer this family to any other providers/specialists for evaluation/treatment? Yes/No
  - If yes, "What other professionals would you refer this child to? Check all that apply."
    - Nutritionist/dietician, gastroenterologist, otolaryngologist (ENT), aerodigestive clinic, pulmonologist, occupational therapist, speech language pathologist, psychologist/social worker, applied behavior analyst (ABA), allergist, multidisciplinary feeding team, other (list)

In addition to the clinical questions, the following questions will be asked in order for the participant to evaluate the tool:

- With a likert scale of completely agree, agree, neither agree nor disagree, disagree, completely disagree
  - The Clinical Feeding Guide meets my approval
  - The Clinical Feeding Guide is appealing to me
  - I like the Clinical Feeding Guide
  - I welcome the Clinical Feeding Guide
  - The Clinical Feeding Guide seems fitting
  - The Clinical Feeding Guide seems suitable
  - The Clinical Feeding Guide seems applicable
  - The Clinical Feeding Guide seems like a good match
  - The Clinical Feeding Guide seems implementable
  - The Clinical Feeding Guide seems possible
  - The Clinical Feeding Guide seems doable
  - The Clinical Feeding Guide seems easy to use
- If you could make changes to the CFG you would (check all that apply):

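### The second primary endpoint counts a referral only to an OT or SLP as a yes, so it cannot be read as the specialist referral that the hypothesis concerns

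*Combined protocol and SAP*

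**What the plan says.** Section 3 defines the second primary endpoint as the yes/no answer to "Would you refer this family to any other providers/specialists for evaluation/treatment". The stated reason for the endpoint is to learn whether the tool "changes decisions therapists make around recommending referral to a specialist". The Synopsis hypothesis is that "the support tool will change whether providers will recommend specialist referral", and Section 4.1 also frames the hypothesis around specialist referral.

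The checklist in Section 6.1.1 has four headings (gastrointestinal, nutritional, behavioral, aerodigestive). Its closing line tells the therapist that "referral to a medical specialist, in addition to your treatment, may be warranted".

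Under Section 8.1, a therapist who answers yes is then asked "What other professionals would you refer this child to? Check all that apply". The options include "occupational therapist, speech language pathologist, psychologist/social worker". The third primary endpoint in Section 3 is built on this follow-up question, and its list also contains both therapy disciplines.

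Section 9.4.2 analyses each case separately. For the yes/no endpoint it plans descriptive reporting, plus a chi-square test if the assumptions are met. For the third endpoint it plans only the percentage of therapists naming each provider, with and without the tool. The term specialist is not defined anywhere.

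**The concern.** Every participant is an OT or an SLP, so referral to the other discipline is open to all of them. A therapist whose only referral is to an OT or SLP scores a full yes on the second primary endpoint, the same as one who refers to gastroenterology. The endpoint therefore mixes two things: the specialist referral that the tool prompts, and referral within the two therapy disciplines, which no checklist heading addresses.

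What is at stake is interpretation. A small difference on this item could mean that the tool does little, or that OT/SLP-only referral already fills the yes category without it. A large difference could partly reflect more OT/SLP-only referral with the tool. The item alone cannot separate these, and it is the only referral endpoint for which a test is planned.

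**Working it through.** **Inputs from the documents.** Sections 6.3 and 9.2 give four cells of 14: 14 × 4 = 56, which reproduces the planned total. Each sequence has 28 therapists. Within one case the comparison is therefore 28 without the tool v 28 with it. Section 9.4.1 specifies two-tailed tests. Section 9.2 bases the sample size on funding and balance, so there is no power figure to reproduce.

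**Assumed inputs.** Alpha is 0.05. The true rate *s* of at least one non-OT/SLP referral is 50% without and 80% with the tool. The share *r* of the remaining therapists who still refer to an OT or SLP is varied. None of these values is in the documents.

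**Formula.** The any-provider yes rate is *s* + (1 − *s*)*r*. With the same *r* in both conditions, the visible difference is (*s*₁ − *s*₀)(1 − *r*). Power is for the uncorrected chi-square test by exact enumeration at 28 v 28.

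| r, both conditions | Yes without tool | Yes with tool | Difference (points) | Power |
|---|---|---|---|---|
| 0 | 50% | 80% | 30 | 67% |
| 0.1 | 55% | 82% | 27 | 61% |
| 0.2 | 60% | 84% | 24 | 53% |
| 0.4 | 70% | 88% | 18 | 37% |
| 0.6 | 80% | 92% | 12 | 26% |

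For example, at *r* = 0.2: 0.50 + 0.50 × 0.2 = 0.60 and 0.80 + 0.20 × 0.2 = 0.84.

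**Whether the test would be run.** Take the usual rule that every expected cell count should be at least 5; Section 9.4.2 does not name its rule. The chance of breaking it is 0.1% at *r* = 0, 23% at *r* = 0.4 and 75% at *r* = 0.6. The test may therefore drop out where dilution is heaviest.

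**If r differs by condition**, with the same true 50% v 80%:
- *r* = 0.5 without the tool and 0 with it: 75% v 80%, 5 points, power 7%.
- *r* = 0.2 without and 0.6 with: 60% v 92%, 32 points, power 84%.
- *r* = 0 without and 0.5 with: 50% v 90%, 40 points, power 94%.

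The first nearly erases a true 30-point effect. The other two overstate it.

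**Can the third endpoint fill the gap?** No. Its percentages come from a check-all item on which choices overlap. If 30% tick gastroenterologist and 30% tick nutritionist (illustrative figures), the proportion ticking at least one of the two can lie anywhere from 30% to 60%. The proportion with at least one non-OT/SLP referral has to be derived per therapist.

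**The case against.** The strongest reply is that the mismatch is less clean than it looks. The objective is titled referral recommendations, and the hypotheses in Section 9.1 speak of referral recommendations without limiting them to specialists. The endpoint that does carry specialist in its title itself lists "occupational therapist, speech language pathologist, psychologist/social worker, applied behavior analyst (ABA), or allergist". On that reading an OT or SLP is a specialist and the item measures what was intended. This stands in part: excluding OT and SLP is not the only documented reading. It does not remove the problem, because the Synopsis hypothesis, the endpoint's justification and the checklist's reference to a medical specialist in addition to the therapist's own treatment point the other way. Inconsistent use of the word is itself a reason to define it.

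Second, a shift towards particular specialists would appear in the third primary endpoint. That is correct, and the information is collected. What is missing is the composite, and nothing in that endpoint is tested.

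Third, this is a pilot with mainly descriptive reporting and no power claim. That also stands. The power figures only show how far the contrast can move; the same distortion affects the descriptive percentages.

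A reader might go further and infer that the broad item does hide a tool effect, or that therapists who add a specialist to an OT referral are recorded as unchanged. The documents support neither. They give no rates, the bias can reverse, and each therapist sees one case without the tool and the other case with it, so no therapist's change on the same case is observed under any definition.

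**Conclusion.** The concern holds as a mismatch between endpoint and hypothesis. As defined, the second primary endpoint is referral to any provider and should not be reported as specialist referral.

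Its numerical effect is conditional. With OT/SLP-only referral equally common in both conditions, the difference shrinks by the factor (1 − *r*): negligibly when *r* is near zero, and by more than half at *r* = 0.6. With unequal shares the endpoint can understate or overstate the specialist effect. All of this rests on the assumed 50% v 80%, the assumed *r* and alpha 0.05, so the actual size is unknown. The point merits a change before analysis because the change is cheap and lets the trial answer its stated question.

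**What to change.** In Sections 3 and 9.4.2:

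- Define specialist.
- Prespecify, per case, a derived yes/no outcome: at least one ticked option other than occupational therapist or speech language pathologist, with 0 for anyone who answered No to the referral question.
- State that the Section 8.1 option list governs. It has two options that the Section 3 list lacks: multidisciplinary feeding team and other (list). Count the feeding team as specialist. Classify the free text under other by a rule fixed before analysis and applied without knowledge of tool condition, since it may name another therapist.
- Use the derived outcome to answer the specialist-referral hypothesis, and report the raw any-provider item beside it.

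The cost is one derived variable from data already collected, a small coding step for free text and a few lines of wording. The survey does not change.

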### 9.4.2 ANALYSIS OF THE PRIMARY EFFICACY ENDPOINT(S)

For the following primary outcomes: degree of concordance between therapists' feeding therapy recommendations and degree of concordance between therapists' referral recommendations we have categorical data (2 groups – using tool and not using tool; 2 answers – yes or no). This is a repeated measure (therapists answer once for case A and once for case B). Each case will be analyzed separately. Due to the categorical data and small sample, reporting will be descriptive. Chi square tests will also be run if determined to meet the required assumptions. For chi-square tests, p value and effect size will be reported. These will be independent and therefore, adjustment for multiple comparisons will not be pursued.

For the third primary endpoint, degree of concordance between therapists' specific specialist referral recommendations, descriptive statistics will be used due to the multiple categories, small counts, and small sample size. The percentage of therapists recommending a particular provider will be compared among therapists using and not using the tool.

Across all analyses, missing data will be reported but not corrected for due to the small sample size. Participants who did not complete all survey items will not be included in analysis. Adjustment for multiple comparisons is considered unnecessary due to the small sample size and minimal use of inferential statistics.

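### The only referral endpoint with a planned test is any-referral yes/no, which cannot register added specialists; the specialist tick-list, already the third primary endpoint, has no per-therapist summary or interval

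*Combined protocol and SAP*

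**What the plan says.** Section 3 makes the second primary endpoint a single yes/no answer per case to "Would you refer this family to any other providers/specialists for evaluation/treatment". The synopsis frames the hypothesis the same way: "We hypothesize the support tool will change whether providers will recommend specialist referral".

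The third primary endpoint, also in section 3, is the tick-list "What other professionals would you refer this child to? Check all that apply". Its stated purpose is to learn whether the tool "changes the specialists a therapist refers to". Section 3 lists ten options. Section 8.1 lists twelve, adding a multidisciplinary feeding team and a free-text other. Both lists include occupational therapist and speech language pathologist.

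Section 9.4.2 treats the two endpoints differently. Each case is analysed separately. The yes/no item is reported descriptively, with a chi-square test, p value and effect size if the test's assumptions hold; no fallback is named. For the tick-list, "descriptive statistics will be used due to the multiple categories, small counts, and small sample size", and the comparison is this: "The percentage of therapists recommending a particular provider will be compared among therapists using and not using the tool". No per-therapist summary, test or interval is given.

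Section 6.1.1 describes a checklist with four headings: gastrointestinal, aerodigestive, behavioral and nutrition. "Under each heading there is a list of observable symptoms that may warrant referral to a specialist provider in that area".

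Section 9.2 bases the sample size on funding: 56 therapists, 28 per sequence. No power, effect size or expected referral rate appears.

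**The concern.** The checklist works by specialty. One plausible effect is that a therapist who would have referred to one specialist now refers to two or three. The yes/no item scores that therapist as yes under both conditions, so the only referral endpoint with a planned test cannot register the change.

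A high yes rate without the tool is plausible, though undocumented. Respondents have at least two years of pediatric feeding experience (section 5.1), are already "expected to screen the medical, nutritional, and psychosocial domains, and make appropriate external referrals" (section 2.1), and are reading a feeding case. One referral of any kind is enough, including an SLP referring only to an OT.

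If the rate is high, the yes/no item has little room to rise and its chi-square test will often not qualify to be run. Evidence about widening would then rest on ten or twelve separate provider percentages per case, none with an interval. No planned result would say how much referral changed per therapist. A pilot should help show which measure can respond to the tool before a larger study.

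**Working it through.** **Inputs from the documents.** There are 4 × 14 = 56 therapists. Within each case, 28 answer with the tool and a different 28 without it (sections 6.3, 9.2 and 9.4.2). Tests are two-tailed (section 9.4.1). The sample size is a count set by funding, so there is no power figure to reproduce.

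**Assumptions.** Alpha 0.05 (not stated), and all referral rates (none are given; a range is shown).

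**1. How many no answers are needed for p < 0.05?** Take the most favourable result for the tool: all 28 users say yes and k of the 28 non-users say no.

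- Uncorrected chi-square = 56 × (28k)² / [28 × 28 × (56 − k) × k].
  - k = 3: 56 × 84² / (784 × 53 × 3) = 3.17, p = 0.075.
  - k = 4: 56 × 112² / (784 × 52 × 4) = 4.31, p = 0.038.
- Two-sided Fisher p = 2 × C(28,k) / C(56,k).
  - k = 4: 2 × 20,475 / 367,290 = 0.11.
  - k = 5: 2 × 98,280 / 3,819,816 = 0.051.
  - k = 6: 2 × 376,740 / 32,468,436 = 0.023.

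So the rate without the tool must be 24/28 (86%) or lower for chi-square, or 22/28 (79%) or lower for Fisher.

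**2. Would the chi-square be run?** With equal groups, the expected number of no answers per group is half their total. The usual condition of at least 5 in every cell therefore needs at least 10 no answers (and 10 yes answers) among the 56. Exact enumeration of two binomials with n = 28 gives:

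| Yes rate without v with tool (assumed) | Expected no answers of 56 | Chi-square power, run regardless | Fisher power | Chance condition is met |
|---|---|---|---|---|
| 50% v 80% | 14 + 5.6 = 19.6 | 67% | 57% | 99.9% |
| 60% v 90% | 11.2 + 2.8 = 14 | 76% | 66% | 93.5% |
| 80% v 95% | 5.6 + 1.4 = 7 | 43% | 21% | 15% |
| 90% v 99% | 2.8 + 0.28 = 3.08 | 24% | 4% | 0.1% |

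**3. What would a per-therapist count add?** For one extra specialist on average, the normal approximation at 28 v 28 gives power of 96%, 85%, 70% and 46% for assumed SDs of 1.0, 1.25, 1.5 and 2.0.

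A simulation (4,000 runs, ten options, therapist random effect on the logit scale) scored the same responses both ways:

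| Any referral, without v with tool | Mean number ticked | Fisher on yes/no | Mann-Whitney on count |
|---|---|---|---|
| 55% v 79% | 0.8 v 1.6 | 39% | 71% |
| 86% v 95% | 2.1 v 3.2 | 6% | 69% |
| 93% v 98% | 2.8 v 3.8 | 0.5% | 55% |
| 90% v 96% (wider spread) | 2.9 v 3.9 | 2% | 39% |

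**4. Where the count does worse.** All rows above assume that the tool adds ticks across the list. Two other effects were simulated with four specialty categories:

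- The tool only moves non-referrers to one referral (50% v 80% any-referral): Fisher 56%, chi-square 66%, count 25%. The count figure depends on how many specialties the existing referrers name.
- The tool only swaps specialties (probabilities 0.7, 0.5, 0.3, 0.1 become 0.3, 0.5, 0.3, 0.5, so the mean is 1.6 in both): the count has 5%, which is no more than alpha.

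**The case against.** The strongest reply is that the yes/no item matches the synopsis hypothesis, which concerns whether providers refer, and that a change in which specialists are chosen already has its own primary endpoint. Both statements are correct. A reader might infer that the trial would miss a widening of referral altogether. The documents do not support that, because it would appear in the provider percentages. What remains is narrower: those percentages have no interval and no per-therapist summary.

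A reader might also infer that the yes/no item is known to sit at its ceiling. No rate and no case text are given, and at 50% or 60% without the tool the item has reasonable power. Nor does the plan say that a flat result means no effect. Reporting is descriptive, and near the ceiling the conditional chi-square would usually produce no p value at all. The endpoints are also framed as concordance, so near-unanimous yes answers in both groups would be informative in themselves.

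A third tempting inference is that a count is simply the better measure. Step 4 of the working shows otherwise: it loses to the yes/no item for the very effect that the synopsis names, and it is blind to swaps. It is also not a measure of agreement. This stands, and it is why the count should be supportive and should replace nothing.

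**Conclusion.** The point holds as a gap in the analysis of data already being collected; the endpoint itself is not wrong. The yes/no item cannot register added specialists, whatever the baseline rate. Whether it also lacks room to move depends on an undocumented rate. From about 80% upwards, the planned chi-square would usually fail its expected-count condition (met 15% of the time at 80% v 95%, and 0.1% at 90% v 99%). At 50% to 60%, a 30-point rise is detected with 67% to 76% power by chi-square.

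When the tool adds specialties, the simulated count had 39% to 71% power where the yes/no item had 0.5% to 39%. That advantage depends on the assumed spread and kind of effect, and it reverses when non-referrers merely become single referrers. All power figures assume a two-sided alpha of 0.05 and 28 completers per group.

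**What to change.** Keep the yes/no item and the provider percentages as they are. In section 9.4.2:

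1. For the third primary endpoint, add a supportive analysis by case: the number of listed professionals ticked per therapist (0 if the answer to referral is no), with v without the tool. Use Mann-Whitney, which fits the nonparametric rule in section 9.4.1, with an effect estimate and 95% CI.
2. Give 95% CIs for the difference in yes rates and for each provider-percentage difference, so that swaps between specialists stay visible.
3. Name Fisher's exact test for the yes/no item when any expected count is below 5.
4. First reconcile the option lists in sections 3 and 8.1. Before responses are opened, state how the feeding team and other options count, and report the feeding-team percentage separately.

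Two further additions may look attractive but are not recommended. One is a count by checklist heading: OT, SLP, allergist and feeding team have no evident single heading. The other is a fixed rule that declares a ceiling when fewer than 6 of 28 say no: it would relabel 24/28 v 28/28 (chi-square p = 0.038) and would ignore decreases, although the tests are two-tailed.

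The cost is analysis-plan wording, one derived variable and one more supportive result per case, with no new data. The remaining weakness is that the count treats a feeding-team referral as a single tick.
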